12.4 Approval from Ethics Committee or Regulatory Authority

The Clinical Investigation Plan (CIP) and the proposed PIC must be reviewed and approved by a properly constituted Ethics Committee (EC) before the start of the investigation. A signed and dated statement from the EC that the CIP and PIC have been approved by the EC must be given to Implandata Ophthalmic Products GmbH before study initiation.

The study must be reviewed and approved by the responsible Regulatory Authorities (RA) before study initiation, according to local and national regulations, if required. When an approval process is not required by the Regulatory Authority at least a notification shall be performed. Any additional requirements imposed by the EC or Regulatory Authority will be followed.

If any alterations, other than changes of an administrative nature only, are made to the study CIP, a formal CIP amendment will be issued and submitted to the relevant EC and RA for approval. The amendment will not be implemented until EC and RA approval, except in cases where immediate implementation is necessary to eliminate or prevent imminent hazard to the subjects.

12.5 Investigator Responsibilities for Ethics Committees and Regulatory Authorities

Prior to study start, the investigator is required to sign a CIP signature page confirming his or her agreement to conduct the investigation in accordance with all of the instructions and procedures found in this CIP and associated documents and to give access to all relevant data and records to Implandata Ophthalmic Products GmbH, monitors, auditors, Quality Assurance representatives, designees, Ethics Committees, and regulatory authorities as required. If an inspection of the investigational site is requested by a regulatory authority, the investigator must immediately inform Implandata Ophthalmic Products GmbH that this request has been made.

Page 91 of 97

12.6 Reporting responsibilities

12.6.1 Investigator Reporting Responsibilities

The investigator or designee is responsible for completing (including review and signature) and submitting to the sponsor all case report forms, as well as reports of any AEs (according to country-specific collection requirements), deaths or deviations from the clinical investigation plan. If any action is taken by the EC with respect to the investigation, the investigator will forward the information to the sponsor as soon as possible. Reports are subject to inspection and to the retention requirements as described in Section 11.3. Refer to Tables Table 2 and Table 3 for SAE reporting responsibilities.

12.6.2 Sponsor Reporting Responsibilities

The sponsor is responsible for reporting SAEs, interim or annual safety reports, premature termination or suspension of the clinical investigation, and the Final Study Report. Refer to Table 3 for details.

12.7 Insurance

The sponsor will maintain appropriate clinical trial liability insurance coverage as required under applicable laws and regulations and will comply with applicable local law and custom concerning specific insurance coverage. If required, proof of the clinical trial insurance policy will be provided to the Ethics Committee. If required by national regulations, indemnification will be provided.

12.8 Amendments to the CIP

The sponsor will inform the investigator about any relevant changes to the CIP. Changes will be documented as an amendment to the CIP that will be signed by each investigator. Unless required to prevent harm to a subject, no changes to the CIP may be implemented by the investigator before a fully approved amendment is available. If applicable due to the nature of the amendment and in accordance with local regulations, EC and RA notification and/or approval is also required before the amendment is implemented.

The investigator is expected to take any immediate action required to ensure the safety of any subject included in this study, regardless of any need for approval of formal CIP amendments, even if this action represents a deviation from the CIP. In such cases, the sponsor should be notified of this action promptly and the Ethics Committee responsible for the study site should be informed.

12.9 Recording, Reporting and Analysis of CIP Deviations

Deviations will be documented in writing and maintained in the Investigator Site File (ISF) and Trial Master File (TMF). The site will report all deviations, regardless of whether medically justifiable or taken to protect the subject in an emergency, to the sponsor in a timely manner on a protocol deviation form. In addition, the investigator is required to adhere to the Ethics Committee procedures for reporting deviations.

Deviations include, but are not limited to the following list:

- Failure to obtain informed consent prior to conducting study specific activities
- Incorrect version of the PIC used
- Subject did not attend treatment visit, or visit was outside the required timeframe
- CIP-required testing and/or measurements were not done or were done incorrectly
- SAEs or SADEs were not reported by investigators within the required timeframe as specified in the CIP
- Source data permanently lost
- Pregnancy of a subject

A sponsor representative or monitor will review site compliance with regard to deviations at each monitoring visit. The monitor will discuss any deviations that occurred at the investigational site directly with the investigator and will summarize the findings in a follow-up letter to the site. In addition, all deviations from the CIP will be documented in the final study report.

12.10 Corrective and preventive action and principal investigator disqualification criteria

See section 12.9 Recording, Reporting and Analysis of CIP Deviation. After analyzing and taking corrective actions, site personnel will be retrained by the sponsor or its representatives on the relevant study procedures. All necessary measurements will be taken to prevent re-occurrence of the protocol deviation. If an investigational site continues to deviate from the CIP despite retraining, the site will be discontinued from the study.

12.11 Suspension or Premature Termination

The sponsor may temporarily or permanently discontinue the study at a single site or at all sites for safety, ethical, compliance or other reasons. If it is necessary to discontinue the study, the sponsor will

Page 93 of 97

endeavor to provide advance notification to the site. If the study is suspended or discontinued, the investigator or the sponsor will be responsible for promptly informing the ethics committee. The monitor will visit the site to conduct a study site closure visit.

12.12 Criteria for access to a breaking/masking code in the case of suspension or premature termination of the clinical investigation, if applicable

This is an open-label study and will not be masked.

12.13 Subject follow-up requirements

All pregnancies will be followed up to birth. All on-going AEs will be followed-up until resolution or until 7 days after the last subject has been discharged from the study. All SAEs will be followed-up until resolution or stabilization.

12.14 Investigator and Site Selection

Site selection will be based on the site's experience with and access to patients requiring nonpenetrating glaucoma surgery. Sites need to meet the following criteria:

- Compliance:
 - Willing to comply with the Clinical Investigation Plan (CIP), all required procedures, the Declaration of Helsinki, ISO 14155 and national and local regulations
- Expertise
 - Investigator experienced in performing non-penetrating glaucoma surgery and in the care of glaucoma patients
 - Access to the patient population
- Patient recruitment potential
 - Potential of 2 8 subjects in the given timeline
 - Patient enrollment and site commitment not expected to be impacted by any competing studies
- Clinical support staff
 - Study nurse/assistant/coordinator or equivalent with adequate training and time to perform study administration including data entry
- Time investment
 - Sufficient availability of the investigator to fulfill the study requirements, including reporting and attendance at the study meetings.

- Equipment / Procedures
 - Separate rooms to perform study procedures
 - Sufficient, lockable storage capacities for study materials

13. PUBLICATION POLICY

13.1 Study Report and Publication

The sponsor is responsible for generating a Clinical Investigation Report (CIR) for the study after the study is completed. This report, or parts of it, will be submitted to the relevant authorities as applicable.

A CIR will be submitted to BfArM within 12 months after completion or premature termination of the clinical investigation in accordance with the German MPG §23a. See Table 3 in section 11.8 for further details.

13.2 Publication of Study Results

The publication of study results will be agreed between the sponsor and the investigator(s). The sponsor is interested in publishing the results of the study, but to prevent publication of any confidential information, the sponsor retains the right to review all publications and presentations before they are made public.

4.6.2	Safety endpoints	24
4.6.3	Further endpoints	24
4.7	Other topics of data analysis: Coding	25
5 Mock	k-up tables and figures	26
6 Refe	rences	30

1 Abbreviations

A	
ADE	Device-related AE
AE	Adverse event
AS	
AS	Anterior Segment
C	
ССТ	Central corneal thickness
CIP	Clinical Investigation Plan
CRF	Case report form
CRO	Clinical Research Organisation
D	
DCT	Pascal Dynamic Contour Tonometry
E	
eCRF	electronic case report form
G	
GAT	Goldman Applanation Tonometry
M	
MMRM	Mixed Model repeated measurement
N	
NEI-VFQ	National Eye Institute Visual Function Questionnaire-25
0	
ОСТ	Optical coherence tomography
ОРА	Ocular Pulse Amplitude
P	
	Dephasian Commant
PS	Posterior Segment

S

SADE Device-related SAE

SAE Serious adverse event
SAP Statistical Analysis Plan

V

V Visit

VFQ-25 National Eye Institute – Vision related Quality of Life Questionnaire-25

2 Summary of clinical investigation

2.1 Title

A first in man, prospective, open-label, single arm, multicenter clinical investigation to assess the safety and performance of the ARGOS-SC suprachoroidal pressure sensor system in patients with glaucoma undergoing non-penetrating glaucoma surgery (ARGOS-SC01)

2.2 Study type

Interventional study

2.3 Study design

Single arm, open label, multicenter, prospective, clinical investigation

2.4 Inclusion Criteria

- 1. Subjects able to understand the informed consent and willing to participate as evidenced by providing informed consent.
- 2. Male or female aged ≥ 18 years on the day of screening. Female subjects of childbearing potential (not surgically sterilized or more than one year post-menopausal) must be willing to use adequate contraception throughout the trial and must have a negative pregnancy test (urine beta-hCG) within 24 hours prior to ARGOS-SC pressure sensor implantation
- 3. Diagnosis of open angle glaucoma requiring a non-penetrating glaucoma surgery (NPGS). The medical indication for a non-penetrating glaucoma surgery must be given irrespective of the study participation. Potential study patients will be solicited for participation in the clinical trial only after the patient has given consent to the non-penetrating glaucoma operation.
- 4. Subjects able and willing to attend all scheduled visits and comply with all study procedures.

2.5 Exclusion Criteria

- 1. Contraindications for a non-penetrating glaucoma surgery
 - a. Neovascular glaucoma, primary and secondary angle closure glaucoma
 - b. Condition after previous glaucoma incisional surgery
 - c. IOP > 40 mmHg
- 2. Myopia (> -6 dpt) or hypermetropia (> +4 dpt)
- 3. Axis length < 22 mm or > 26 mm
- 4. Patient with single eye vision (monovision)
- 5. Exudative age-related macular degeneration, instable macular degeneration 30 days prior to inclusion, or macular edema
- 6. Acute retinal detachment
- 7. Uncontrolled Diabetes Mellitus (DM) with manifestation of moderate to severe non-proliferative diabetic Retinopathy (DR) or proliferative DR.
- 8. History or evidence of severe active inflammatory eye diseases (i.e. uveitis, retinitis, scleritis) in one or both eyes within 6 months prior to ARGOS-SC implantation
- 9. Ocular surgery procedure(s) (excluding selective laser trabeculoplasty and peripheral iridotomy) within 6 months (cataract surgery within 3 months) prior to ARGOS-SC implantation in the study eye that can affect the assessment of IOP by Goldmann Applanation tonometry
- 10. Ocular disease other than glaucoma that may affect assessment of visual acuity and/or IOP by Goldmann Applanation tonometry/Pascal Dynamic Contour Tonometry (e.g. choroidal hemorrhage or detachment, lens subluxation, thyroid ophthalmopathy)
- 11. Existence of other active medical eye implant and/or other active medical implants in the head/neck region
- 12. Difficulties or complications during NPGS procedure or implantation of ARGOS-SC sensor, as assessed by surgeon (e.g. perforation of trabeculo-descement's membrane; excessive aqueous filtration through TDM leading to shallow anterior chamber; excessive bleeding; choroidal detachment)
- 13. Severe generalized disease resulting in a life expectancy shorter than a year
- 14. Currently pregnant or breastfeeding
- 15. Participation in any study involving an investigational drug or device within the past 30 days or ongoing participation in a study with an investigational drug or device

- 16. Patients who are not suitable for the study based on the surgeon's evaluation (e.g. patients affected by Parkinson's disease or essential tremor)
- 17. Patients unable or unwilling to understand or comply with required study procedures
- 18. Patients with psychiatric disorders influencing their judgement or autonomy
- 19. Subject and/or an immediate family member is an employee of the investigational site directly affiliated with this study, the sponsor or the contract research organization.
- 20. Enrollment of the fellow eye in this clinical study

2.6 Study population

Patients with glaucoma and scheduled for non-penetrating glaucoma surgery

2.7 Study objective

2.7.1 Primary objective

Performance:

To evaluate the limits of agreement between measurements with Goldmann Applanation Tonometry (GAT), Pascal Dynamic Contour Tonometry (DCT) and the ARGOS-SC system in the 12 months following implantation.

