3.3 Advantages of Experimental Treatment

The ARGOS-SC system that is the subject of this investigation is anticipated to provide a feasible solution to these problems. It is a multicomponent system consisting of the ARGOS-SC device, an intraocular pressure sensor that is intended to be permanently implanted in the patient's suprachoroidal space during the non-penetrating glaucoma surgery, and the MESOGRAPH, an external handheld reader that powers and interrogates the ARGOS-SC implant telemetrically. Because the sensor itself is in direct contact with the choroid, it measures IOP directly from the vitreous throw the force on the choroid, without interference from either the cornea and sclera, or physical contact with the external eye. The device is easy to use, permitting patients or their immediate caregivers to measure IOP themselves in the home setting several times per day. The IOP measurements so obtained are stored in the Mesograph memory and can be accessed by the treating ophthalmologist, either directly from the Mesograph during patient visits or between visits when uploaded by the patient using the accessory Multiline Connector to a central database. The implantation itself, as a part of the nonpenetrating glaucoma surgeries, doesn't elongate or complicate the surgery itself, as many other implantation procedures for IOP sensors do. Therefore, the sensor gives extra benefit with multiple feasible IOP-measurements without creating and extra risk for the patient by extended operating times and special implantation entrance or manipulation.

The related EYEMATE-IO system, which is implanted in the sulcus and received CE-mark approval in 2017, has been shown to effectively measure IOP in glaucoma patients who underwent cataract surgery [12], with an accuracy comparable to that of GAT.

Although developed using the same materials and technology as the EYEMATE-IO, the form and location of placement of the ARGOS-SC differ sufficiently to require independent clinical investigation. The present investigation, which is the first-in-human, will test its use in patients with glaucoma undergoing concurrent indicated NPGS. If shown to be safe and accurate, it is anticipated that the ARGOS-SC system will permit a detailed tracking of IOP levels in this patient population, thereby facilitating timely adjustments medication while at the same time, ultimately reducing the number of control visits required of patients.

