8.2.2 Justification of the choice of comparator

GAT, considered by the medical community to be the gold standard method of IOP measurement, will be used as comparator. However, GAT actually estimates IOP based on a measurement of the force needed to applanate a predetermined area of the cornea while the ARGOS-SC sensor will be in direct contact with the aqueous humor and measure IOP directly. Consequently, differences are anticipated between the IOP values obtained with the two devices. However, trends in IOP are expected to remain the same regardless of the method used. Therefore, to assess the accuracy of the ARGOS-SC system, IOP profiles obtained with ARGOS will be compared to those obtained with GAT.

Pascal DCT is designed to eliminate some of the measurement errors in GAT that come from variations in corneal thickness and rigidity. It is believed to be closer to true IOP, especially at higher IOPs. It is also less prone to "user error".

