2.9 Study endpoints

2.9.1 Primary endpoints

Performance:

Level of agreement between measurements made using GAT and the ARGOS-SC system at visit V02 - V09.

The concordance of the intraindividual measurement values of GAT and ARGOS-SC will be indicated by the concordance correlation coefficient r_{ccc} (4.6.1), separate for each visit

Additionally, the absolute difference between the GAT and ARGOS-SC measurement will be scaled in \leq 5mmHg and > 5 mmHg and the frequency distribution will be displayed (4.6.1, Table 2).

The Bland-Altman (mean-difference) plot and a X-Y plot should illustrate the comparison of the two methods (4.6.1, Figure 1).

The level of agreement between Pascal DCT and ARGOS-SC will be evaluated analogously.

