- Calculation of the average of the (up to) 3 IOP measurements using ARGOS-SC (ARGOS1_{mean})
- Calculation of the average of the (up to) 3 IOP measurements using DCT (DCT_{mean})
- Calculation of the average of the (up to) 3 IOP measurements using OPA (OPA_{mean})
- Calculation of the average of the (up to) 3 IOP measurements using ARGOS-SC (ARGOS2_{mean})
- Difference IOP_{d1}= ARGOS1_{mean} GAT_{mean}
- Mean IOP_{mean1} = (ARGOS1_{mean} + GAT_{mean})/2
- Difference IOP_{d2}= ARGOS2_{mean} DCT_{mean}
- Mean IOP_{mean2} = (ARGOS2_{mean} + GAT_{mean})/2

 $ARGOS1_{mean}$ / GAT_{mean} / IOP_{d1} (statistical parameters, concordance correlation coefficient r_{ccc} , Bland-Altman-Plot with IOP_{mean1} vs. IOP_{d1} , plot of $ARGOS1_{mean}$ vs. GAT_{mean}), separate for each visit

 $|IOP_{d1}| \leq 5 \text{ mmHg (N, \%)}$

ARGOS2_{mean} / DCT_{mean} / IOP_{d2} (statistical parameters)

 $|IOP_{d2}| \leq 5 \text{ mmHg (N, \%)}$

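### The plan names GAT, DCT and ARGOS-SC together but never compares GAT with DCT, so sensor disagreement is judged only against a fixed limit and not against how well two tonometers agree in the same eyes

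*SAP*

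**What the plan says.** The primary objective (SAP 2.7.1; Protocol 7.1.1) is "To evaluate the limits of agreement between measurements with Goldmann Applanation Tonometry (GAT), Pascal Dynamic Contour Tonometry (DCT) and the ARGOS-SC system". The protocol's primary endpoint (8.1.3.1) covers GAT and ARGOS-SC at V02 to V04, and all three methods at V05 to V09.

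SAP 2.9.1 turns this into two comparisons. The first is "Level of agreement between measurements made using GAT and the ARGOS-SC system at visit" V02 to V09. The second is given in one sentence: "The level of agreement between Pascal DCT and ARGOS-SC will be evaluated analogously". SAP 4.6.1 forms the visit averages, including "Calculation of the average of the (up to) 3 IOP measurements using DCT", and then two differences: IOP_d1 (ARGOS1 minus GAT) and IOP_d2 (ARGOS2 minus DCT). No GAT-DCT difference, limit of agreement, concordance coefficient or plot appears in either document. The only formula in the DCT block that contains GAT is "Mean IOP_{mean2} = (ARGOS2_{mean} + GAT_{mean})/2". That looks like a slip in the horizontal axis of the DCT plot and is not a comparison of the tonometers.

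The measurement order in Protocol 8.3.13.14 is GAT (2 or 3 readings), ARGOS-SC (3), then at V05 to V09 where available DCT (2 or 3) and ARGOS-SC again (3).

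The success criterion in Protocol 9.5 uses GAT and ARGOS-SC only: 70% of measurements within ±5 mmHg.

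**The concern.** Protocol 8.2.2 expects ARGOS-SC to differ from GAT. It explains this by saying that GAT only estimates pressure from corneal applanation, whereas "the ARGOS-SC sensor will be in direct contact with the aqueous humor and measure IOP directly". Protocol 3.3 describes the contact differently: "Because the sensor itself is in direct contact with the choroid". Protocol 4.2 places the implant between sclera and choroid. Section 5 records the worry that this slightly indirect measurement might not represent the true pressure, and 4.8.1.4 allows drift of up to 2.5 mmHg a year. On the sponsor's own text, a disagreement could come from either side.

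Protocol 8.2.2 includes DCT because it should remove some cornea-related GAT error. GAT against DCT is therefore the natural yardstick: does ARGOS-SC disagree with GAT more than a second established tonometer does, in the same operated eyes at the same visits? The data to answer this are collected, but the analysis is not planned. If the primary result is middling, a GAT-DCT comparison added afterwards would look like a search for an explanation.

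**Working it through.** **1. The plan's own figure.** Protocol 9.2 gives a minimum of approximately 120 measurements. A one-sample proportion test with p0 = 0.70 (9.1.4), two-sided α = 0.10 (SAP 4.1.4), 80% power (9.3) and an assumed p1 = 0.80 gives

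n = [(1.645·√0.21 + 0.842·√0.16) / 0.10]² ≈ 119.

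This agrees with the protocol, but p1 is not in the documents and repeated pairs are treated as independent. The figure concerns GAT against ARGOS-SC and is not in dispute here.

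**2. GAT-DCT pairs available.** There are 24 patients and 5 visits (V05 to V09), so 24 × 5 = 120 pairs at most, and fewer where DCT is not available. That this equals the figure in step 1 is coincidence. The pairs are clustered within at most 24 patients.

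**3. What the benchmark adds.** Assume normal differences with zero bias. The share within ±5 mmHg is 2Φ(5/SD) − 1.

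- SD 3.4: 2Φ(1.47) − 1 ≈ 86%.
- SD 2.0: 2Φ(2.50) − 1 ≈ 99%.

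Take ARGOS-GAT at SD 3.4, close to the 3.38 in the SAP's V05 mock-up, which is used here only as an assumption. The 86% passes the 70% criterion whatever GAT-DCT shows. If GAT-DCT has SD 3.4, the sensor is about as far from GAT as another tonometer is. If it has SD 2.0, the sensor is clearly further away. The planned outputs do not separate these cases.

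**4. How far the third pair can attribute error.** With independent errors on a common scale, sensor error variance = (Var d1 + Var d2 − Var d3)/2, and GAT error variance = (Var d1 + Var d3 − Var d2)/2, where d3 = DCT − GAT. All SDs below are assumed.

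| SD d1, d2, d3 (mmHg) | Sensor error SD | GAT error SD |
|---|---|---|
| 3.4, 3.4, 2.0 | √[(11.56 + 11.56 − 4)/2] = 3.09 | √[(11.56 + 4 − 11.56)/2] = 1.41 |
| 3.4, 2.5, 3.4 | √[(11.56 + 6.25 − 11.56)/2] = 1.77 | √[(11.56 + 11.56 − 6.25)/2] = 2.90 |

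The ARGOS-GAT SD is the same in both rows, and the attribution reverses.

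**5. The independence assumption.** Let GAT and DCT each have error variance 8, with correlation 0.75 (assumed), and let the sensor have error variance 3.56. Then

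- Var d1 = Var d2 = 3.56 + 8 = 11.56 (SD 3.4)
- Var d3 = 8 + 8 − 2(0.75)(8) = 4 (SD 2.0)

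These are exactly the SDs of the first row, but now the sensor error SD is √3.56 = 1.9 and the GAT error SD is √8 = 2.8. Even all three pairwise SDs do not settle the split unless the correlation is known.

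**6. Precision at one visit.** The 95% half-width of a limit of agreement is t·SD·√[1/n + 1.96²/(2(n − 1))].

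- n = 24: 0.73 SD, or 2.5 mmHg at SD 3.38.
- n = 12: 1.12 SD, or 3.8 mmHg.

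In a simulation with a true sensor share of 50% (error SDs: sensor and GAT 2.39, DCT 2), the central 95% of estimated shares ran from 17% to 83% with 24 patients, and from about 0% to 100% with 12. Pooling visits would narrow this by an amount that depends on within-patient correlation, which the documents do not give.

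**The case against.** A GAT-DCT contrast is not clearly required. The objective names three methods without listing pairs, and Protocol 3.3, 8.1.2 and 8.2.1 describe the sensor against each tonometer, which is what the SAP does. This stands. The case rests on interpretation of the primary result and does not show that the SAP breaks its objective.

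A reader might infer that the trial has no benchmark and that its ±5 mmHg result cannot be interpreted. The documents do not support this. The protocol sets 70% within ±5 mmHg (9.1.4, 9.5) and cites a ±5 mmHg tonometer tolerance (4.8.1.4) and a ±5 mmHg repeat-measurement imprecision (3.2). Only an empirical tonometer-against-tonometer benchmark is missing.

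A reader might also infer that the disagreement cannot be divided between sensor and tonometer. That is too strong as well. The GAT-DCT difference can be derived from the collected data, and sensor repeatability is a planned endpoint (SAP 2.9.2). Pre-clinical tests compared the sensor with set pressures: R² of 0.99 or better in porcine eyes, and mean bias of 0.01 to 0.62 mmHg in rabbits (Protocol 4.8.1.2, 4.8.2.1). These answer the question only in part. Three consecutive readings show short-term noise but not a patient-specific offset or drift, and the pre-clinical tests were not in living human eyes.

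The strongest objection is to the variance split. GAT and DCT may share corneal error, since 8.2.2 says DCT removes only some of it. Readings are unmasked, and an ARGOS-SC series separates the two tonometers, so a real pressure change between them inflates Var d3 and lowers the estimated sensor error. With steps 5 and 6 above, this rules the split out as a main result. It does not count against a plain descriptive GAT-DCT table.

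**Conclusion.** The point holds as a gap in the planned analysis, not in the design. Two of three available pairs are analysed, so ARGOS-SC disagreement is set against a fixed limit and not against the agreement of two established tonometers in the same operated eyes. At most 120 clustered pairs from at most 24 patients are left unused. The pass/fail rule does not change; what changes is how the primary agreement result can be read. The size of that effect is unknown, because every SD used above is an assumption. The descriptive comparison needs no independence assumption, but its limits will be wide. Separate error variances would rest on independent errors and equal scale, and would be too imprecise to support a firm conclusion.

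**What to change.** In SAP 4.6.1, add IOP_d3 = DCT_mean − GAT_mean at V05 to V09, at visits where DCT is available. Report bias, limits of agreement and the share within ±5 mmHg, as for IOP_d1. Show d1, d2 and d3 side by side on the same visits, so that sites without DCT do not distort the comparison.

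State three limits with the table: at most 24 × 5 = 120 pairs exist; they are clustered within at most 24 patients; and GAT and DCT are separated by an ARGOS-SC series. Report ARGOS2_mean − ARGOS1_mean as a check on pressure shift between the series.

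If per-method error variances are wanted, label them exploratory, give patient-level intervals, and show a sensitivity range for correlated GAT and DCT errors.

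Separately, reconcile Protocol 8.2.2 with 3.3 on what the sensor touches. While SAP 4.6.1 is open, also reconcile the GAT term in IOP_mean2 with the DCT pair it belongs to.

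The cost is a few lines of SAP text and one table, with no new measurements. Making the change before database lock keeps it prespecified.
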